1.1.3 Clofarabine & Ara-C in AML

Clofarabine inhibits RNR, and is a superior substrate for dCK, with increased cytotoxic effects *in vitro* compared to fludarabine and cladribine, and therefore may be an appropriate combination agent with Ara-C^{36,38,39}. *In vitro* studies suggest that clofarabine is more effective at increasing Ara-CTP in leukemic blasts than fludarabine⁴⁹. Therefore, the combination of clofarabine and Ara-C is theoretically attractive, and several such combinations have been studied in AML in both the relapse/refractory and newly-diagnosed populations.

An MDACC phase I/II pilot study of clofarabine & 'intermediate dose' Ara-C (1g/m²/day x 5) in relapsed/refractory AML patients demonstrated that the combination was reasonably well tolerated, although grade III/IV toxicity was observed, including diarrhea (n=4,

20%), rash (n=2, 10%), impaired liver function (n=2, 10%), hand-foot syndrome (n=1, 5%) and palpitations/arrhythmia (n=1, 5%). A febrile episode associated with myelosuppression was experienced by 20 patients (63%) including 1 treatment-related death from bacterial sepsis. The overall response rate was 38%⁵⁰.

The combination of clofarabine & intermediate-dose Ara-C was subsequently evaluated in a phase II study in 60 *newly-diagnosed* patients with AML and high grade MDS at the MTD of clofarabine (40mg/m² d1-5)⁵¹. The median age was 61 years (range 50-74). Myelosuppression following treatment was 'ubiquitous', and there were 9 deaths on study (15%), virtually all related to infectious complications. The most frequent side effects were diarrhea, emesis, palmoplantar erythrodysesthesia, and reversible liver function test abnormalities (most commonly grade III/IV hyperbilirubinemia and elevation in transaminases). The CR rate was 52%, and another 5 achieved CRp (8%). At a median follow-up of 18 months, the median duration of CR and CRp were 8 months and <2 months, respectively. Median overall survival was 10 months, while the median survival of patients achieving CR was almost 2 years.

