Because long-term cures have been observed in previous studies with the same patient population, we assume a cure rate mixture distribution for the standard arm, with the distribution on the clofarabine arm given by a proportional hazards shift from the standard arm, to calculate power. Based on a previous ECOG study, E3999, we assume that the long-term cure rate in the standard treatment arms will be 10% and median survival among the non-cured group will be about 9 month, i.e., the survival model for the standard treatment arm $S_0(t) = 0.1 + 0.9 \exp(-t^* \log(2)/9)$. The study team would consider clofarabine to be acceptable if the long-term cure rate in the clofarabine arms will be no lower than 8% and median survival among the non-cured group will be no less than 8 months, which is approximately a less than 12% increase in hazard rate. Therefore, our null hypothesis is that the hazard ratio for clofarabine/standard is no less than 1.12. The alternative is that the hazard ratio for clofarabine/standard is no more than 0.86. The non-inferiority of clofarabine will be tested at a one-sided significance level of 0.025.

We assume that 8% of those patients will undergo allogeneic transplant. We also assume that 25% of patients who do not receive allogeneic transplant go through the second randomization. Adjusted for the sequential monitoring described below and based on the weighted analysis previously described, with 685 patients, the study will have approximately 80% power to reject the null hypothesis of inferiority of clofarabine at the one-sided significance level of 0.025 under the alternative above, assuming 5 years of accrual and 2 years of follow-

up after the completion of accrual. The size and power of the study will not be affected even if the proportions of patients receiving maintenance are imbalanced between the induction arms. The full information needed is 507 events. This information is the expected number of deaths among the non-allo non-decitabine patients under the alternative. Deaths on the decitabine maintenance arm do not contribute information to this comparison. Since the allo transplant patients are censored at the time of transplant, they do not contribute events. Therefore, the overall sample size was increased by 1/(1-0.08), around 9%, to make up for the loss of information. A total accrual of 747 patients is planned for this study.

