The intention-to-treat approach will be used in this analysis. Patients with donors who choose not to have AlloSCT (or are unable due to insurance issues) need to be included in the AlloSCT arm for analysis. Assuming that 50% of patients receiving chemotherapy in induction and consolidation achieve a 'morphologic leukemia-free state' and 25% of those patients have a donor, 94 patients from the allogeneic transplant arm and 280 patients from the chemotherapy arms will be available for this OS comparison.

For the chemotherapy arms, we assume that the long-term cure rate will be 10% and median survival among the non-cured group will be about 9 months. The

study will have 82% power to detect approximately a 32% reduction in the OS hazard rate in the allogenic transplant arm using one-sided log-rank test at the significance level of 0.025. This power calculation assumes 5 years of accrual and 2 years of follow-up after the completion of accrual. Full information needed is 292 deaths. The analysis of this secondary objective will use a one-sided log rank test stratified on age, therapy-related AML, the presence of AHD at the time of diagnosis of AML, and the induction therapy they received.

Rev. Add10

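### The donor comparison in Section 9.4 is powered with the survival curve of all randomised patients, although it includes only those who reach a leukemia-free state, so the stated 82% power is optimistic

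*Combined protocol and SAP*

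**What the plan says.** Section 9.2 sets the curve for the primary OS comparison: "we assume that the long-term cure rate in the standard treatment arms will be 10% and median survival among the non-cured group will be". The figure that completes this sentence is 9 months, and the curve is written as 0.1 + 0.9·exp(−t·log 2/9). It applies to the standard arm as randomised, with OS counted from randomisation.

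Section 9.4 then defines who enters the transplant comparison: "Assuming that 50% of patients receiving chemotherapy in induction and consolidation achieve a 'morphologic leukemia-free state", of whom 25% have a donor. This gives the sizes: "94 patients from the allogeneic transplant arm and 280 patients from the chemotherapy arms will be available for this OS comparison". For the chemotherapy group it states "we assume that the long-term cure rate will be 10% and median survival among the non-cured group will be about 9 months", and concludes that the "study will have 82% power to detect approximately a 32% reduction in the OS hazard rate in the allogenic transplant arm". The test is a log-rank test, one-sided at 0.025, with 5 years of accrual and 2 years of follow-up. It adds: "Full information needed is 292 deaths". Section 9.4 gives no reason for reusing the curve and does not state the OS time origin for this comparison.

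**The concern.** The curve in Section 9.2 contains induction deaths and refractory disease. The group in Section 9.4 has been selected by getting past both. If all patients and the responding half share one curve, the non-responding half must share it too.

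The plan's other statements do not fit that:

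- Section 1 attributes the poor survival of older patients mainly to primary chemotherapy resistance, seen in low remission rates.
- Section 9.4 assumes 10% mortality by day 30 on standard treatment. The outcome marrow is taken between days 28 and 56 (Section 5.1.4), so nearly all of those deaths fall outside the leukemia-free group.
- Under Section 5.1.1, patients without a response after a second induction leave the study.

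Log-rank power depends on deaths. If leukemia-free-state patients live longer than the curve says, fewer deaths occur within 5+2 years. A null donor result would then be read against a power that the comparison does not have.

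**Working it through.** **Inputs (Section 9.4 unless noted).** 94 donor and 280 no-donor patients; hazard ratio 0.68; one-sided 0.025; uniform accrual over 60 months plus 24 months of follow-up; control curve 10% cured with a 9-month non-cured median (also Section 9.2); 50% response. The donor-group curve is S₀(t)^0.68.

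**1. Reproduce the stated power.**

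Schoenfeld: donor share p = 94/374 = 0.2513, p(1−p) = 0.1882, |ln 0.68| = 0.3857.
Power = Φ(√(292 × 0.1882) × 0.3857 − 1.960) = Φ(7.41 × 0.3857 − 1.960) = Φ(0.899) = 81.6%.

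Log-rank integrated over risk sets: Y₀ = 280·S₀·G and Y₁ = 94·S₀^0.68·G, where G = 1 up to 24 months and (84 − t)/60 after that; w = Y₁/(Y₀ + Y₁); h₀ is the control hazard.
E = ∫[0.68Y₁ − w(0.68Y₁ + Y₀)]h₀dt, V = ∫w(1−w)(0.68Y₁ + Y₀)h₀dt, power = Φ(|E|/√V − 1.960).
The plan's curve gives 81.7% power and about 314 expected deaths.

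So 82% follows from the printed inputs by either route. Schoenfeld at the 314 deaths expected by year 7 gives 84%.

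**2. What the shared curve implies.** With 50% response, S_all = 0.5·S_R + 0.5·S_NR, so S_NR = 2·S_all − S_R. Setting S_R = S_all gives S_NR = S_all. Induction deaths and failures would then be 10% cured, with a median OS of 9 × log₂(0.9/0.4) = 10.5 months, the same as responders.

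**3. Responder curves consistent with Section 9.2.** Set S_R = 2·S_all − S_NR. The documents give no S_NR. I assume 0-5% of non-responders cured and a median of 5-7 months in the rest. The responders' cure rate is then 20% minus that of the non-responders.

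| Non-responders cured | Responders cured | Deaths at 5+2 years | Power, log-rank | Power, Schoenfeld |
|---|---|---|---|---|
| 0% | 20% | 265-269 | 74% | 78% |
| 3% | 17% | 277-281 | 76% | 79-80% |
| 5% | 15% | 284-288 | 77-78% | 81% |

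Compared like with like, log-rank power falls from 82% to 74-78%, and Schoenfeld power at year-7 deaths falls from 84% to 78-81%.

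**4. Wider assumed range, not tied to Section 9.2.** Simple cure mixtures for responders, with non-cured medians of 9, 12, 15 and 18 months:

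| Cured | Deaths | Power, log-rank (%) | Power, Schoenfeld (%) |
|---|---|---|---|
| 15% | 295, 283, 270, 256 | 78.7, 76.8, 74.5, 71.9 | 81.9, 80.4, 78.4, 76.3 |
| 20% | 276, 265, 253, 240 | 75.5, 73.6, 71.3, 68.8 | 79.4, 77.8, 75.8, 73.6 |

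**5. Ceiling on deaths with unlimited follow-up.** 280(1 − c) + 94(1 − c^0.68). At c = 0.20: 224.0 + 62.5 = 286.5, below 292. At c = 0.15: 238.0 + 68.1 = 306.1, above it.

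**The case against.** The strongest reply is that this challenges an assumption and not the arithmetic, and that the documents fix no replacement. That is correct. Three stronger readings are tempting, and the documents do not support them.

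- **A reader might infer that the true power is about 75%.** That value needs a 20% cure rate and the integrated log-rank method. Schoenfeld, which also reproduces the printed figure, gives 78-79% in the same case. The 20% is contestable: Section 1.3 reports fewer than 15% long-term disease-free survivors among patients in CR, and Section 9.4 itself assumes a 10% cure rate for DFS in patients still in remission after consolidation. The mismatch could also mean that the 10% for all patients in Section 9.2 is too high.
- **A reader might infer that 292 deaths will not occur.** With 15% cured and a 9-month median, about 295 are expected and 292 is reached by year 7 with probability about 67%. With 20% cured and the same median the probability is at most about 4%.
- **A reader might infer that the analysis waits for 292 deaths.** Section 9.4 calls them the information needed, not a trigger, and also gives a 5+2-year horizon. Survivors are followed for at least 5 years (Section 5.7). If 292 deaths did accrue, Schoenfeld power would be 81.6% whatever the curve; at the ceiling of about 287 it is about 81%.

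The background study in Section 1.1.3, "Median overall survival was 10 months, while the median survival of patients achieving CR was almost 2 years", is only weak support. It is one phase II study of a clofarabine-cytarabine combination in patients aged 50-74, and CR is narrower than leukemia-free state.

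The 94/280 split is uncertain too. Section 3.2.9 admits unrelated donors while Section 9.4 describes an HLA-identical sibling. For illustration, a 35% donor share with 276 deaths would give about 86% by Schoenfeld.

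What stands against the reply is the internal conflict. The 15%/9-month case still gives non-cured non-responders the same survival as non-cured responders. Solved consistently with Section 9.2, 15% cured responders give 284-288 expected deaths and 77-78% log-rank power.

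**Conclusion.** The point holds as a conflict between two of the plan's own assumptions. Sections 9.2 and 9.4 give one curve to all randomised patients and to the responding half, and the direction of the error is optimistic.

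Within curves consistent with Section 9.2 and 50% response, power for a 32% reduction is about 74-78% by log-rank (78-81% by Schoenfeld), with about 265-288 deaths at 5+2 years. These figures rest on assumed non-responder survival (0-5% cured, median 5-7 months) and hold the 94/280 split fixed. Over the wider assumed range they are 240-295 deaths and 69-82% power across the two methods. No single value is established by the documents.

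The shortfall is a few points on a secondary objective. It matters because Section 1.2 presents the donor comparison as a distinctive contribution of the trial.

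**What to change.** In Section 9.4:

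1. Replace the 10%/9-month curve with one for patients in a leukemia-free state. Either derive it from the Section 9.2 curve and 50% response, with the non-responder assumptions stated, or fit it to the pooled OS of such patients among the 727 already accrued (Section 9.5), blind to donor status.
2. State the OS time origin for this comparison.
3. Restate power and expected deaths as a range, in the mid-to-high 70s percent rather than 82%, and name the formula used.
4. Tie the analysis to the stated 2 years of follow-up after accrual rather than to 292 deaths.

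The cost is one recalculation and some wording, with no extra patients or procedures. The downside is a stated power a few points less favourable. Sections 9.5, 9.6 and 9.8 already contain figures based on the 727 patients, so the transplant calculation can be updated in the same way.

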5.1.8 Maintenance

5.1.8.1 Observation vs. Decitabine Maintenance (2nd Randomization) – Arm E and Arm F

Patients who complete consolidation therapy will undergo restaging with a BM aspiration & biopsy and repeat BM cytogenetics to confirm CR or CRI. Patients will then be randomized to maintenance therapy with decitabine vs. monthly observation for 12 months.

- Decitabine 20 mg/m²/day IV over 1 hour QD x 3 days, repeated Q4 weeks x 12 months total⁷⁵, up to 13 cycles, but not to continue beyond 12 months. Regardless of treatment delays, the total duration of maintenance therapy will be 12 months.
- There are no planned dose reductions in decitabine. Patients unable to receive treatment on schedule (i.e. planned q4 weeks, but delays up to 4 weeks allowed) due to cytopenias or persistent side effects will discontinue decitabine and subsequently be observed per the 'observation' group (Arm E), although they will be analyzed on an 'intention to treat' basis as having been assigned to Arm F.
- The ANC must be > 1000 mm³ and the platelet count > 75,000 mm³ prior to starting every cycle of treatment with decitabine. Decitabine may be delayed for up to 4 weeks between cycles (i.e. may be administered as infrequently as q8 weeks) while waiting for counts to recover.
- Monthly CBC and examination will be performed on all patients assigned to decitabine or observation for 24 months

Rev. 8/13

5.1.8.2 Patients who do not meet eligibility for Randomization to Observation vs. Decitabine Maintenance after recovery from Consolidation should be followed according to Arm E.

5.2 **Adverse Event Reporting Requirements**

5.2.1 **Purpose**

Adverse event data collection and reporting, which are required as part of every clinical trial, are done to ensure the safety of patients enrolled in the studies as well as those who will enroll in future studies using similar agents. Adverse events are reported in a routine manner at scheduled times during a trial (please refer to the E2906 Forms Packet for the list of forms with directions for routine adverse event reporting). Additionally, certain adverse events must be reported in an expedited manner for more timely monitoring of patient safety and care. The following sections provide information about expedited reporting.

5.2.2 **Determination of Reporting Requirements**

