9.2 Primary Endpoint and Sample Size

The primary objective of this trial is to determine the effect of clofarabine on overall survival in comparison with standard therapy. The primary endpoint is overall survival (OS). OS is defined as the time between randomization and death from any cause. Patients last known to be alive at the time of an analysis will be censored.

The primary comparison of OS will be based on the treatment assignment received at randomization. To reduce potential bias of the primary comparison from the alloSCT arm, the patients will be censored at the time of allogeneic transplant for the primary analysis. Due to the potential confounding by maintenance therapy on the induction comparison, a weighted analysis (weighted Cox regression) (121,122,123) will be used for the primary analysis. Let π denote the actual proportion randomized to the observation arm of all patients entering on maintenance randomization. In the weighted analysis, patients who do not enter maintenance randomization get weight 1; Observation maintenance arm patients get weight $1/\pi$. Decitabine maintenance arm patients get weight 0. Thus, patients on the observed maintenance arm represent themselves as well as the response of $(1/\pi - 1)$ similar patients in the decitabine maintenance arm. A robust variance estimator that correctly accounts for the weights will be used in this setting.

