9.6 AML Clinical Epidemiology

We assume that approximately 600 (82% of all 727 registered to Step 1) patients will complete the ALESE questionnaire. The proportions of obese patients and patients who had benzene exposure, ever smoked in their lifetime, took aspirin regularly, took acetaminophen regularly, ever lived in rural/farm environments, or had other exposures or lifestyle factors will be calculated separately, along with their 95% CIs. With 600 patients, the width of the 95% CI will be no wider than 0.08.

We will examine the impact of smoking, obesity, regular acetaminophen use, regular aspirin use, benzene exposure, and living in a rural/farm environment on OS. The impact of some other exposures or lifestyle factors on OS will also be explored. Assume 50% patients ever smoked in lifetime and assume for those patients a 10% long-term cure rate and 8-month median overall survival in the non-cured group. With treatment arms combined, the study will have approximately 80% power to detect a 22% reduction in the hazard rate in non-smoking patients, using a one-sided log rank test at the significance level of 0.025 and assuming 2 years of follow-up. The number of events needed is 502. Assume 20% patients had benzene exposure and assume those patients have a 10% long-term cure rate and 7.5 -month median overall survival in the non-cured group. With treatment arms combined, the study will have approximately 80% power to detect a 27% reduction in the hazard rate in non- benzene- exposure patients, using a one-sided log rank test at the significance level of 0.025 and assuming 2 years of follow-up. The number of events needed is 482. When data are available, a one-sided log-rank test stratified by induction treatment effect will be used to evaluate the impact of those exposures or lifestyle factors on OS. Moreover, the weighted analysis as described in Section [9.2](#) will also be used in order to reduce the potential bias from the maintenance therapy. Patients receiving alloSCT will be included in this analysis.

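### The donor versus no-donor OS test in Section 9.4 makes no allowance for decitabine, which falls mostly in the no-donor group; add the Section 9.2 weighted analysis beside the log-rank test

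*Combined protocol and SAP*

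**What the plan says.** Section 9.4 compares OS by intention to treat between patients with and without a donor. Donor patients who are not transplanted stay in the transplant group. The sizes are given as "94 patients from the allogeneic transplant arm and 280 patients from the chemotherapy arms will be available for this OS comparison". The chemotherapy group is modelled with 10% cured and a 9-month median in the rest, and the plan states that the "study will have 82% power to detect approximately a 32% reduction in the OS hazard rate in the allogenic transplant arm"; the test level is one-sided 0.025. It adds: "Full information needed is 292 deaths". The analysis is then fixed: "The analysis of this secondary objective will use a one-sided log rank test stratified on age, therapy-related AML", antecedent hematologic disorder and induction therapy. No weight, stratum, censoring rule or sensitivity analysis for maintenance is mentioned.

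Section 5.1.8.1 describes what follows consolidation for patients still in remission: "Patients will then be randomized to maintenance therapy with decitabine vs. monthly observation for 12 months". Section 9.1 limits this step to patients who are not transplanted.

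Elsewhere the plan does deal with maintenance. Section 9.2 says: "Due to the potential confounding by maintenance therapy on the induction comparison, a weighted analysis" is used for the primary OS comparison, with weight 0 for decitabine patients, 1/π for observation patients (π being the proportion randomized to observation) and 1 for all others, with a robust variance. Section 9.6 tests exposures by a stratified log-rank test and says that the same weighted analysis "will also be used in order to reduce the potential bias from the maintenance therapy".

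**The concern.** Objective 2.2.2 sets transplant against patients receiving chemotherapy. Section 1.3 calls observation the standard and decitabine the experimental option. The no-donor group in 9.4 is nevertheless part chemotherapy followed by observation and part chemotherapy followed by decitabine.

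The imbalance is larger here than in the induction comparison, for which 9.2 introduced the weights. The induction arms are randomized and maintenance is stratified by induction arm, whereas transplant and maintenance are alternative routes at Step 3 (Section 4.4). The control survival model in 9.4 is the one 9.2 uses for the standard arm, so the 82% power builds in no decitabine benefit.

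If decitabine prolongs survival, the transplant effect shrinks towards 1 and power falls. If decitabine shortens survival, transplant looks better than it is. Section 9.4 specifies no analysis that would separate the two.

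**Working it through.** **Inputs from the documents.** 94 versus 280 patients, 292 deaths, hazard ratio (HR) 0.68, one-sided 0.025, 10% cured and 9-month median, 5 years' accrual plus 2 years' follow-up (9.4). 8% transplanted (9.2). 172 second randomizations planned (9.4), 86 of them to decitabine (9.8). 120 second randomizations among 727 patients reached (9.5), so about 60 on decitabine. Planned decitabine DFS HR 0.64 (9.4).

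**Assumptions.** Decitabine's OS HR is not in the documents; 0.64 (carried over from DFS), 0.80 and 1.0 are used. The second randomization is placed about 4.5 to 7.5 months after the OS origin.

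**1. The plan's own figure.** Power = Φ(|ln HR| × √(D·p·(1−p)) − 1.96), with D = 292 and p = 94/374 = 0.251. The root is √(292 × 0.251 × 0.749) = 7.41. For HR 0.68, 0.386 × 7.41 − 1.96 = 0.90, so power is 81.6%. The stated 82% reproduces.

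**2. Where decitabine patients fall.** 8% of 747 is about 60 transplants against 94 donor patients, which leaves about 34 untransplanted donor patients who could reach maintenance. Two cases bracket this: decitabine spread over the no-donor and untransplanted donor patients, or all of it in the no-donor group. Scaled to 727 patients, the groups are 91 and 273 (727 × 0.5 = 363.5, a quarter with a donor). Spreading 60 decitabine patients puts about 7 in the donor group and 53 in the no-donor group.

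**3. Hand check of the apparent HR.** With f1 and f0 the decitabine shares in the donor and no-donor groups and h the decitabine OS HR, apparent HR ≈ 0.68 × h^(f1 − f0).
- 120 randomized, spread: f1 − f0 = 7/91 − 53/273 = −0.117. For h = 0.64 this gives 0.72; for h = 0.80, 0.70.
- 120 randomized, all no-donor: f0 = 60/273 = 0.220. For h = 0.64 this gives 0.75; for h = 0.80, 0.71.
- 172 randomized, all no-donor: f0 = 86/280 = 0.307. For h = 0.64 this gives 0.78.

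Putting 0.72, 0.75 and 0.78 into the power formula with 292 deaths gives 68%, 57% and 45%.

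**4. Simulation from the plan's cure model, log-rank test.** The decitabine hazard is multiplied by h after the second randomization.

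| Second randomizations | Decitabine OS HR | Apparent transplant HR | Power |
|---|---|---|---|
| any | 1.0 | 0.68 | 81-82% |
| 120 (reached) | 0.80 | 0.70-0.72 | 69-74% |
| 120 (reached) | 0.64 | 0.72-0.75 | 54-66% |
| 172 (planned) | 0.64 | 0.73-0.78 | 43-61% |

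The milder end of each range has decitabine spread over both groups; the worse end has all of it in the no-donor group.

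**5. With the 9.2 weights.** The estimated HR returns to 0.68. In the null case run (172 randomized, all decitabine in the no-donor group), one-sided type I error is about 2.3%. Power is about 70-76% when decitabine has no OS effect.

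**The case against.** The strongest reply is that 9.4 compares strategies on purpose. Sections 1.2 and 1.2.1 describe a donor versus no-donor analysis by biological randomization, 9.4 specifies intention to treat, and maintenance is the protocol's next step for patients who are not transplanted. On that reading decitabine belongs to the no-donor strategy and is not a confounder. This is a legitimate question, and it is why the log-rank test should stay. But 9.4 does not state it, objective 2.2.2 names chemotherapy as the comparator, and the power model leaves out any decitabine benefit.

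Several other points stand:
- The 36% reduction planned for decitabine is in DFS. No OS effect is planned, and with none the log-rank test keeps its power.
- The imbalance is not wholly one-sided. Section 5.1.7.1 lets donor patients who are unfit or decline transplant go to consolidation, and so possibly to maintenance.
- In 9.6 the weighted analysis supplements the log-rank test and does not replace it.
- Weighting gains power only if decitabine's OS effect is large. At 120 randomized with decitabine spread over both groups, log-rank and weighted power are 81% and 73% at decitabine HR 1.0, 73% and 71% at 0.80, and 65% and 72% at 0.64.

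A reader might infer that a null transplant result could not be told apart from a decitabine benefit. The documents do not support that: Arms E and F are randomized against each other and Section 5.7 follows all patients for survival, so decitabine's OS effect can be estimated directly. A reader might also infer that power falls to one particular figure, such as 57%. That is one point in a range set by an assumed OS effect and by how many untransplanted donor patients enter maintenance.

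**Conclusion.** The gap is real. Section 9.4 leaves decitabine unadjusted in a comparison where it is clearly unbalanced, while 9.2 and 9.6 treat maintenance as a source of bias and provide the tool to deal with it.

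The size is conditional. At the accrual reached, and with an assumed decitabine OS HR between 0.64 and 0.80, a true transplant HR of 0.68 would appear as about 0.70-0.75, with power between 54% and 74%. The planned 172 randomizations would give a larger distortion at HR 0.64, but that number depends on reopening. Section 9.5 makes reopening conditional on an interim result, and the text does not say whether the 52 added patients would join the donor comparison.

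A decitabine benefit makes the test conservative for transplant; decitabine harm would favour transplant. The trial's primary analysis is not affected.

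**What to change.** In Section 9.4, keep the one-sided stratified log-rank test and add the Section 9.2 weighted Cox analysis, following the pattern of 9.6: weight 0 for decitabine, 1/π for observation, 1 for everyone else, robust variance, applied in both the donor and the no-donor group. State that the weighted estimate addresses transplant versus chemotherapy without decitabine, and that the log-rank test compares strategies that include the maintenance randomization. Report the number of decitabine patients in each donor group so that the imbalance is visible.

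The cost is SAP wording and one more model run using weights already needed for 9.2, with no new data. The weighted analysis is less precise: about 70-76% power, against about 81% for the log-rank test when decitabine has no OS effect. Both results should therefore be reported.
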